6.3 Carboplatin

6.3.1 Carboplatin may be administered as a substitution for cisplatin when cisplatin-related toxicities occur as described in 6.3 Cisplatin Dose Modification for Toxicity or when patients present with $>$ grade 2 sensory or motor neuropathy, $>$ grade 2 hearing loss, or <60 ml/min calculated creatinine clearance at baseline.

6.3.2 The first dose of carboplatin, AUC=2 IV, will be administered within the first 3 days of the start of RT and repeated weekly during the 7 weeks of RT. The last dose of chemotherapy may be given up to one week following completion of RT. If RT is held, carboplatin will also be held.

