	Appendix 2 – Head and Neck MD Anderson Symptom Inventory (MDASI-HN)	48
	Appendix 3 – Xerostomia Questionnaire.....	50
	Appendix 4 – Penetration/Aspiration Scale.....	52
	Appendix 5 – Montreal Cognitive Assessment	53
	Appendix 6 – MD Anderson Dysphagia Inventory (MDADI).....	54

SCHEMA

Treatment Plan:

The protocol combines *selective* RT dose de-escalation (from 70 Gy to 63 Gy and from 58.1 Gy to 50.75 Gy, same number of fractions (N=35) in 7 weeks) in patients with HPV-associated cancers of the oropharynx receiving standard of care treatment based on clinical stage. Image guided RT with daily cone-beam CT imaging will be used with CTV to PTV margins of 5 mm. Outcome will be evaluated both in terms of tumor control (and pattern of failure) and toxicity/QoL. Endpoints: Prevalence of grade 3+ toxicity at 2 yrs according to CTCAE 4.0 <15%; locoregional control at 2 yrs >85%.

SCC oropharynx, HPV positive,

Tx, T1-2 and Nx (without ECE), N0-1, N2a (<5 cm) → de-escalated IMRT alone ± S for residual disease

T3 and/or Nx (with ECE) N2a (≥5 cm), N2b-c, N3 (resectable) → de-escalated IMRT + conc CDDP ± S for residual disease

Eligibility:

- Confirmed histopathologic diagnosis of oropharyngeal (*tonsil, base of tongue, pharyngeal wall, soft palate*) squamous cell carcinoma;
- Human papillomavirus (HPV) positive;
- Stage T1-T3, N0-N3 (resectable), M0; both sides of the neck are judged to be at risk of metastatic disease
- Surgery of the primary tumor is limited to incisional or excisional biopsies; any surgery is allowed in the neck; patients with surgery at both primary and nodal sites and without macroscopic residual disease (cTxcNx) are excluded)
- ANC \geq 1200 /mm³
- Platelets >100,000/ mm³
- Adequate hepatic function with bilirubin < 1.5 mg/dl
- AST < 2x the upper limit of normal
- ALT < 2x the upper limit of normal
- Serum creatinine < 1.3 mg/dl
- Normal serum calcium (or normal corrected serum calcium)
(Please note*: Formula for corrected calcium if albumin value is below normal range: Corrected calcium (mg/dl) = [4 – [patient albumin (g/dl)] x 0.8 + patient calcium (mg/dl)
- Cannot have Serum creatinine >1.3 or ULN
- Cannot have CCL < 60 cc/min
- ECOG performance status 0-1
- Nutritional condition must be considered compatible with the proposed radiotherapeutic treatment (cannot have unintentional and/or surgically unrelated weight loss >20% in the preceding 3 months)
- Patients cannot be a current smoker at time of treatment

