3.1.3 Negative pregnancy test for women of childbearing potential

3.1.4 T stage: 1, 2, 3. Surgery of the primary tumor is limited to incisional or excisional biopsies (i.e. tonsillectomy) even without macroscopic disease left. Positive resection margins and/or gross residual disease at the *primary* site are allowed; evaluation of primary tumor extent may require the use of a flexible fibroscope if deemed clinically necessary by the treating physician; any N stage but resectable; lymph nodes in both sides of the neck are at risk of metastatic disease, according to clinical judgment, and require irradiation; pre-treatment surgery in the neck in the forms of incisional/excisional biopsy or a multilevel neck dissection is allowed only if there is gross tumor left at the primary site;

3.1.5 No other malignancy except for non-melanomatous skin cancer, early stage prostate cancer (T<2a and PSA<10 and GLS<7) or a carcinoma not of head and neck origin disease free for > 5 yrs.

3.1.6 - ANC > or = to 1000 /mm³

- Platelets >100,000/ mm³

- Adequate hepatic function with bilirubin < 1.5 mg/dl

- AST < 2x the upper limit of normal

- ALT < 2x the upper limit of normal

- estimated CCL ≥ 60 cc/min

- Normal serum calcium (or normal corrected serum calcium) (Please note*:

Formula for corrected calcium if albumin value is below normal range: Corrected calcium (mg/dl) = [4 – [patient albumin (g/dl)] x 0.8 + patient calcium (mg/dl)

- 3.1.7 Cannot have distant metastasis (M0);
- 3.1.8 ECOG performance status 0-1
- 3.1.9 Patient's nutritional and general physical condition must be considered compatible with the proposed radiotherapeutic treatment (cannot have unintentional and/or surgically unrelated weight loss > 20% in the preceding 3 months). *This assessment is a standard of care assessment for this patient population. This requirement can be waived by the investigator if the subject has an identifiable procedure which is the immediate and sole cause for the weight loss without an underlying pathological cause. An example of a situation like this would be if a participant is found to need a tonsillectomy during the pretreatment evaluations. It's obvious that this scenario would be a non-pathological reason for such a weight loss. The PI will only have this ability to waive this criterion if and only if he can substantiate and document that the weight loss does not have a pathological etiology and will correct itself within a reasonable and acceptable period of time

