3.2 Ineligibility Criteria

- 3.2.1 Evidence of distant metastases.
- 3.2.2 Absence of macroscopic disease after upfront surgery, i.e. TxNx and TxN0. TxN+ and T1-3Nx are eligible if the T/N stage categories meet the criteria of 3.1.1
- 3.2.3 Previous irradiation for head and neck tumor; concurrent chemotherapy other than the treatment per protocol; previous chemotherapy \leq 3 months from start of RT.
- 3.2.4 Active untreated infection.
- 3.2.5 Major medical or psychiatric illness, which in the investigators' opinion would interfere with either completion of therapy and follow-up or with full and complete understanding of the risks and potential complications of the therapy.
- 3.2.6 Use of amifostine or pilocarpine before and during radiotherapy is not allowed.
- 3.2.7 Serum creatinine >1.3 or ULN, CCL < 60 cc/min, Peripheral neuropathy > grade 1, and/or frequency hearing loss that interferes with activities of daily living are contraindications to cisplatin but not to carboplatin (6.2.4).
- 3.2.8 Patients with > 10 pack years of smoking history and/or currently a smoker at the time of treatment.

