4 PRETREATMENT EVALUATIONS

- 4.1 Each patient must have completed the following studies prior to irradiation:
 - 4.1.1 Complete history and physical exam including weight and performance status.

4.1.2 Complete dental evaluation. Any required dental extractions must be made and fluoride prophylaxis instituted prior to radiotherapy.

4.1.3 Speech pathology evaluation including instrumental swallowing assessment or clinical assessment of swallowing and administration of pretreatment swallowing and trismus exercises (*This assessment is a standard of care assessment for this patient population). Completion of pretreatment MD Anderson Dysphagia Inventory (MDADI) and Montreal Cognitive Assessment (MCA). Speech therapy evaluation has to take place before commencement of treatment.

4.1.4 Nutritional evaluation to be conducted within the first week of starting (chemo)radiation therapy.

4.1.5 Completion of the following laboratory studies: CBC with diff. and platelets, Metabolic Panel to include- sodium, potassium, glucose, calcium, magnesium, BUN, serum creatinine, total protein, albumin, alkaline phosphatase, total bilirubin, AST, ALT, and a creatinine clearance)

4.1.6 Completion of the following radiologic studies: CT of head and neck with < 3 mm contiguous slices in immobilization system (*with contrast, unless contraindicated*); whole body PET/CT (integration of both high resolution CT with contrast and dedicated PET acquisition through the head and neck are strongly suggested); MRI of head and neck with gadolinium including T1 and T2 weighted sequences in at least 2 different planes strongly suggested for primary tumors of the base of tongue (*optional-see 5.1.2*).

4.1.7 Audiogram to be conducted before or within the first week of starting therapy (*if inner ear is to be irradiated at mean dose ≥ 40 Gy*).

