6.2 Cisplatin Dose Modification for toxicity

6.2.1 *Hematologic:* Patients must have an ANC ≥ 1000 /mm³ and platelets $>100,000$ / mm³ prior to receiving cisplatin. If the patient's counts are below these levels, cisplatin will not be given and weekly dosing reinstated the following week as long as counts are within acceptable treatment parameters. Held doses will not be made up. Grade 4 neutropenia (ANC <500 /mm³) or febrile neutropenia requiring hospitalization for antibiotics or grade 4 thrombocytopenia (platelets $<25,000$ / mm³) require a dose reduction of cisplatin of 25%.

6.2.2 *Neurotoxicity:* Patients developing grade 2 sensory or motor neuropathy or $>$ grade 2 hearing loss will have cisplatin discontinued and carboplatin substituted (see 6.3.4).

6.2.3 *Nephrotoxicity:* Measurement of serum creatinine is required before each treatment with cisplatin and must be within normal limits. Serum creatinine above the upper limit of normal necessitates creatinine clearance assessment using the modified Cockcroft-Gault formula. If the patient's calculated creatinine clearance is less than 60 ml/min, cisplatin will be held and additional hydration will be given. Serum creatinine and creatinine clearance should be repeated weekly and/or as needed after additional hydration is given. Cisplatin may be reinstated, under the discretion of the treating physician, if the CCl improves to greater than or equal to 60 ml/min. If the creatinine clearance does not improve despite additional hydration, cisplatin will be substituted with carboplatin (see section 6.3.4). Held doses will not be made up.

6.2.4 *Switch to Carboplatin:* In case of any of the followings, cisplatin will be substituted to carboplatin: creatinine clearance < 60 ml/min; ototoxicity; peripheral sensory or motor neuropathy grade 2. Weekly carboplatin dosing would be at AUC=2. Dose modifications of cisplatin and carboplatin will be under the discretion of the treating medical oncologist. If the patient has peripheral neuropathy $>$ grade 1, and/or frequency hearing loss that interferes with activities of daily living, cisplatin can be dose reduced or substituted with carboplatin.

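### Renal entry rules contradict each other: the Schema and 3.1.6 refuse creatinine clearance below 60, while 3.2.7 and 6.3.1 leave such patients a carboplatin route

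*Combined protocol and SAP*

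**What the plan says.** **Renal function at entry**

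- Schema, eligibility list: "Cannot have CCL < 60 cc/min" and "Cannot have Serum creatinine >1.3 or ULN". Neither line is limited to patients due to receive chemotherapy.
- Section 3.1.6: "estimated CCL ≥ 60 cc/min". This also applies to all candidates. It sets no serum creatinine limit.
- Section 3.2.7, within the ineligibility list, names raised serum creatinine (above 1.3 or ULN) and clearance below 60, together with neuropathy and hearing loss. It says that these "are contraindications to cisplatin but not to carboplatin (6.2.4".
- Section 6.3.1 allows carboplatin in place of cisplatin in two situations. One is cisplatin toxicity during treatment. The other is a patient who presents with neuropathy, hearing loss or "<60 ml/min calculated creatinine clearance at baseline".
- Section 6.2.4 separately covers patients already on cisplatin: "cisplatin will be substituted to carboplatin: creatinine clearance < 60 ml/min".

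**N2a nodes**

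- Section 6 opens by reserving chemotherapy for, among others, clinical nodal stage above N1. The bracket that follows counts N2a only from 5 cm upwards.
- The Schema uses the same 5 cm cut in both arms and sends smaller N2a nodes to IMRT alone.
- Sections 1.2 and 1.3 link chemoradiotherapy to single nodes over 3 cm, or to N2 and N3 disease generally, with no 5 cm split.

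**The concern.** Entry criteria should give one answer for each candidate. Here the Schema and 3.1.6 make creatinine clearance below 60 a reason to refuse the patient, whereas 3.2.7 and 6.3.1 make it a reason to choose a different platinum agent. The second treatment of the finding makes sense only if some of these patients can be on study. Part of the conflict lies inside Section 3, between the eligibility and ineligibility lists, so a rule that Section 3 takes precedence over Section 6 would not settle it.

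What is at stake is who is enrolled and who receives platinum chemotherapy with impaired renal function, which bears on patient safety. The N2a inconsistency raises the same kind of question on a smaller scale: whether a patient whose only possible trigger is an N2a node under 5 cm receives chemotherapy.

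**Working it through.** The plan gives no figure to reproduce, so the check applies each passage to the same illustrative patients.

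| Patient | Schema | 3.1.6 | 3.2.7 | 6.3.1 |
|---|---|---|---|---|
| A. Chemotherapy stratum, clearance 55 | Refuse | Refuse | No cisplatin; carboplatin open | Carboplatin may be given |
| B. IMRT-alone stratum, clearance 55 | Refuse | Refuse | Bars cisplatin only, and none is planned | Not relevant |
| C. Chemotherapy stratum, serum creatinine above 1.3, clearance 60 or more | Refuse | Renal criterion met | No cisplatin; carboplatin open | Creatinine not listed |

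**Patient A** is the main conflict. Two passages refuse entry and two describe a treatment route for the same finding.

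**Patient B** shows that the conflict is not confined to chemotherapy. The Schema and 3.1.6 refuse this patient. 3.2.7 ties the same finding to a drug that the patient would not receive.

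**Patient C** shows that serum creatinine is handled in three ways: a bar to entry in the Schema, a bar to cisplatin in 3.2.7, and no criterion in 3.1.6. Here the Schema and 3.1.6 disagree with each other.

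**Could 6.3.1 refer only to changes during treatment?** Its wording joins two cases with an *or*: toxicity from cisplatin, and findings with which the patient presents. The renal finding in the second case is expressly placed at baseline. A fall in clearance during treatment already has its own rule in 6.2.3 and 6.2.4, which does not conflict with the entry criteria. Reading 6.3.1 as an on-treatment rule therefore does not remove the conflict.

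**N2a.** Take a T2 N2a patient with a 4 cm node and no extracapsular extension.

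- Section 6, opening clause: above N1, so chemotherapy.
- Section 6, bracket: under 5 cm, so no chemotherapy.
- Schema: under 5 cm, so IMRT alone.
- Sections 1.2 and 1.3: over 3 cm and N2, so chemoradiotherapy.

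The bracket and the Schema agree with each other. The opening clause and the background text make no such distinction.

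**The case against.** The strongest reply is that 3.1.6 is an explicit entry requirement, while 3.2.7 and 6.3.1 only say which drug may be used and do not expressly admit anyone. On that view a patient below 60 is refused, and the other wording is largely redundant. This is a fair strict reading. It does not remove the conflict, because 3.2.7 sits in the ineligibility list and can be read as an exception, and 6.3.1 then sets out a treatment for the patient.

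On N2a, the bracket directly follows the opening clause and can be taken to specify it, in agreement with both Schema arms. Those who treat Sections 1.2 and 1.3 as background only will find the operative rule fairly clear. That is why this point is secondary.

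A reader might also infer more than the documents support:

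- *That the baseline renal route in 6.3.1 can apply to nobody, because one clearance value serves both for eligibility and as baseline.* Baseline is not defined. Section 4.1.5 lists "alkaline phosphatase, total bilirubin, AST, ALT, and a creatinine clearance" among tests due before irradiation, not before registration. Table 9, note 17, requires clearance weekly in chemotherapy patients. A patient could be eligible at registration and below 60 by the first dose. This narrow route does not resolve the conflict, but it rules out *nobody*.
- *That the timing in 6.3.2, "The first dose of carboplatin, AUC=2 IV, will be administered within the first 3 days of the start of RT", shows that patients below 60 are meant to enrol.* Patients who present with neuropathy or hearing loss would explain that sentence by themselves.
- *That on N2a only the opening clause of Section 6 is out of line.* Sections 1.2 and 1.3 also lack the 5 cm cut.
- *That one affected patient could decide whether a primary goal is met.* One of 50 evaluable patients is 1/50 = 2 percentage points, and the 15% toxicity goal lies between 7/50 (14%) and 8/50 (16%). But this is true of any patient, and Section 10.3.1 only reports the rates with exact 95% intervals. It states no pass/fail count.

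**Conclusion.** The renal entry criteria are internally inconsistent and should be corrected. The Schema and 3.1.6 exclude every candidate with creatinine clearance below 60. 3.2.7 and 6.3.1 leave room to enrol such a patient on carboplatin. Serum creatinine is also treated inconsistently. The N2a mismatch is real but secondary.

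The documents do not give the number of patients affected by either point, so its size cannot be stated. No effect on the two primary endpoints is quantified or claimed. The conclusion rests on comparing the current text and needs no assumed figures. It takes no position on which renal limit or nodal cut is clinically right.

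**What to change.** - Reconcile the Schema, 3.1.6, 3.2.7 and 6.3.1 into one renal eligibility rule that covers both creatinine clearance and serum creatinine.
- State whether that rule applies to patients assigned IMRT alone.
- Reconcile the opening clause of Section 6 with its own bracket, the Schema and Sections 1.2 and 1.3 on N2a nodes.

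The clinical team decides which rule applies in each case. The cost is amendment wording only. The planned 60 enrolled and 50 evaluable patients, the stopping bounds and the primary analysis in Section 10 do not change.

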6.4 Carboplatin Dose Modification for Toxicity

6.4.1 Hematologic: Patients must have an ANC ≥ 1000 /mm³ and platelets $>100,000$ / mm³ prior to receiving carboplatin. If the patient's counts are below these levels, carboplatin will not be given and weekly dosing reinstated the following week as long as counts are within acceptable treatment parameters. Held doses will not be made up. Grade 4 neutropenia (ANC <500 /mm³) or febrile neutropenia requiring hospitalization for antibiotics or grade 4 thrombocytopenia (platelets $<25,000$ / mm³) require a dose reduction of carboplatin of 25%.

6.4.2 Nephrotoxicity: Serum creatinine and creatinine clearance should be checked weekly before each treatment with carboplatin and/or as needed to calculate appropriate carboplatin dose and assess hydration status.

7 SURGERY

7.1 Upfront neck surgery (*excisional biopsy or neck dissection*) is at the discretion of the surgeon.

7.2 Surgery at the primary tumor is expected to consist of an incisional biopsy for diagnostic purposes only. An excisional surgery (i.e. tonsillectomy) is allowed if other gross disease is present e.g. neck lymph nodes. Patient will be also staged according to the clinical stage before any surgical procedure.

7.3 Surgery should be performed for persistent tumor following RT as documented by PET/CT (CT with thin slices and i.v. contrast for the HN part) at 8-12 weeks after the end of the treatment, or at the discretion of the surgeon. Suspected residual disease is defined as persistent FDG uptake at the site of the primary tumor qualitatively assessed by comparing to background and corresponding abnormal tissue on CT. Surgery is recommended for PET/CT positive residual disease, as described. A selective neck dissection is appropriate for patients with positive residual disease in levels II-IV and levels IB and V were initially negative. A comprehensive neck dissection is recommended in the other cases.

8 PATHOLOGY

Tumors will be evaluated for the presence of HPV16 DNA by use of the in situ hybridization – catalyzed signal amplification method for biotinylated probes (GenPoint; Dako, Carpinteria, CA)⁵⁰. The expression status of p16 is strongly correlated with tumor HPV status and therefore it will be evaluated by immunohistochemistry, as previously described⁵¹. For tumors positive at P16 but negative for HPV16, a wide spectrum in-situ hybridization test will be run to exclude infection by less frequent subtypes of HPV (30, 31...). In the latter case, specimens will still be considered HPV positive and therefore eligible for the study.

9 PATIENT ASSESSMENTS

9.1 Patient Assessments

Table 9.

	Pretreatment	During treatment ¹	Follow up ²
Weight & PS	X	X	X
History & Physical	X		
Dental Evaluation	X		
Nutritional evaluation	X ³	X ³	
CBC with diff. and platelet count	X	X ¹⁵	
CMP ¹⁸	X	X ¹⁵	
Creatinine Clearance	X	X ¹⁷	
Pregnancy Test	X ¹⁶		
Thyroid Function Test (TSH)	X		X
PET/CT (CT w contrast)	X		X ⁵
MRI of head and neck	X ⁶		X ⁵
Toxicity Evaluation ⁷	X	X	X
Flexible fibroscope ¹⁰	X		X
Audiogram ¹⁴	X	X	X
Speech therapy evaluation ¹²	X	X ⁸	X ⁹
MBSS			X ¹¹
Biopsy	X ¹³		X ¹³
Appendix 2 & 3	X	X	X

1. Weekly during radiotherapy

2. Follow-up will be performed 6-8 weeks after the end of RT (+ or – 7 days), at 3 months (+ or - 14 days) after the end of radiotherapy and every 3 months thereafter for the first two years; then every 6 months (+ or – 30 days) during years 3 to 5

3. Initial evaluation must be done within a week of starting therapy and then as clinically indicated. On treatment nutrition evaluations will be performed as clinically indicated.

4. Every 6 months for 5 years

5. PET/CT is required at 10-12 weeks after the end of treatment to evaluate response. Afterwards a PET/CT should be obtained at the discretion of treating physician. Alternatively a CT or MRI can be obtained if a PET/CT is not approved.

6. A pre-study MRI is at the discretion of the treating physician

7. See 5.12

8. At approximately the 4th week of treatment

9. To be performed 6-8 weeks, 6 months, and 12 months after the end of RT

10. Primary tumor assessment may require the use of a flexible fibroscope as deemed by the treating physician.

11. To be performed at 6-8 weeks and 12 months even in absence of specific symptoms

12. The MD Anderson Dysphagia Inventory (MDADI) will be given at each visit; the Montreal Cognitive Assessment (MCA) will only be given at baseline and 6-8 weeks after completion

13. Pretreatment Biopsy can be done outside JH provided that pathology blocks are submitted at JH for review and HPV testing; During follow up, any suspicious mucosal lesion in the upper aerodigestive tract should trigger a search for recurrent disease that may or may not include a biopsy; in the latter case, the biopsy can be done at JH or outside, but, again, the pathology specimen must be reviewed at JH. No further HPV testing is necessary on the repeat biopsy.

14. Pre-study audiogram is required if the inner ear is to be irradiated at a dose \geq 40 GY (the audiogram should be done before or within 1 week after starting treatment); subsequent audiograms are under the discretion of the treating physician as indicated by symptoms.

15. Only if concomitant chemotherapy is part of the treatment
16. Only for women of child bearing potential
17. Creatinine clearance (CCL) required weekly for patient receiving chemotherapy.
18. CMP to include: sodium, potassium, glucose, calcium, magnesium, BUN, serum creatinine, total protein, albumin, alkaline phosphatase, total bilirubin, AST and ALT

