2 OBJECTIVES

2.1 To achieve a prevalence of grade 3+ late toxicity at 2 yrs <15% while maintaining a locoregional tumor control >85±7% at the same time interval (toxicity is scored at 5.11 and 9.5 and locoregional control at 9.4);

2.2 To determine the nature and prevalence of side effects at different time intervals and describe their relationship to pretreatment function and local dose and treated volume.

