10.3 Analysis of Endpoints

10.3.1. To achieve a prevalence of grade 3+ toxicities between six months and two years post-treatment <15% while maintaining a locoregional tumor control of at least 85% during the same time interval.

The primary endpoints, prevalence of toxicity and locoregional control rate, will be reported for all patients with an exact 95% confidence interval.

10.3.2. To determine the nature and prevalence of side effects at different time intervals and describe their relationship to pre-treatment function (toxicity) and local dose and treated volume.

Patients will be grouped by whether they had none or a grade 0-2 toxicity versus a grade 3+ toxicity. We will tabulate the frequency of patients in each group by a dichotomous measure of dose and tests for differences with a Chi-square or Fisher's exact test. Patients will also be grouped dichotomously by the number of side effects experienced

and frequencies will be compared to dose category and toxicity category using Chi-square or Fisher's exact tests.

10.3.3. To determine the quality of life of surviving patients.

The results of the Head and Neck MD Anderson Symptom Inventory (MDASI-HN) will be calculated for each patient. The mean score will be reported with a 95% confidence interval. The range and quartiles of the distribution of scores will also be reported.

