
Blood & lymphatic system disorders: Febrile neutropenia
 
Definition: A disorder characterized by a decrease in neutrophils associated with fever.
			
present
	
Life-threatening consequences; urgent intervention indicated
	
Death

Blood & lymphatic system disorders: Anemia
 
Definition: A disorder characterized by an reduction in the amount of hemoglobin in 100 ml of blood. Signs and symptoms of anemia may include pallor of the skin and mucous membranes, shortness of breath, palpitations of the heart, soft systolic
	
Hemoglobin (Hgb) <LLN – 10.0 g/dL; <LLN – 6.2 mmol/L; <LLN – 100 g/L
	
Hgb <10.0 – 8.0 g/dL; <6.2 – 4.9 mmol/L; <100 – 80g/L
	
Hgb <8.0 – 6.5 g/dL; <4.9 – 4.0 mmol/L; <80 – 65 g/L; transfusion indicated
	
Life-threatening consequences; urgent intervention indicated
	
Death

murmurs, lethargy, and fatigability.					
--------------------------------------	--	--	--	--	--

Investigations: White blood cell decreased
 
Definition: A finding based on laboratory test results that indicate an decrease in number of white blood cells in a blood specimen.
	<LLN – 3000/mm ³ ; <LLN – 3.0 x 10 ⁹ /L	<3000 – 2000/mm ³ ; <3.0 – 2.0 x 10 ⁹ /L	<2000 – 1000/mm ³ ; <2.0 – 1.0 x 10 ⁹ /L	<1000/mm ³ ; <1.0 x 10 ⁹ /L	Death

Investigations: Neutrophil count decreased
 
Definition: A finding based on laboratory test results that indicate a decrease in number of neutrophils in a blood specimen.
	<LLN – 1500/mm ³ ; <LLN – 1.5 x 10 ⁹ /L	<1500 – 1000/mm ³ ; <1.5 – 1.0 x 10 ⁹ /L	<1000 – 500/mm ³ ; <1.0 – 0.5 x 10 ⁹ /L	<500/mm ³ ; <0.5 x 10 ⁹ /L	Death

Investigations: Platelet count decreased
 
Definition: A finding based on laboratory test results that indicate a decrease in number of platelets in a blood specimen.
	<LLN - 75,000/mm ³ ; <LLN - 75.0 x 10 ⁹ /L	<75,000 - 50,000/mm ³ ; <75.0 - 50.0 x 10 ⁹ /L	<50,000 - 25,000/mm ³ ; <50.0 - 25.0 x 10 ⁹ /L	<25,000/mm ³ ; <25.0 x 10 ⁹ /L	Death

Respiratory, thoracic, & mediastinal disorders: Voice alteration
 
Definition: A disorder characterized by a change in the sound and/or speed of the voice.
	Mild or intermittent change from normal voice	Moderate or persistent change from normal voice; still understandable	Severe voice changes including redominantly whispered speech; may require frequent repetition or face-to-face contact for understandability; may require assistive technology		Death

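### Section 10.3.2 relates toxicity to radiation dose without separating chemotherapy from IMRT-alone patients, although after baseline only chemotherapy patients have scheduled blood counts

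*Combined protocol and SAP*

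**What the plan says.** **Schedule.** Section 4.1 states "Each patient must have completed the following studies prior to irradiation", and 4.1.5 lists "Completion of the following laboratory studies: CBC with diff. and platelets". In Table 9 the row "CBC with diff. and platelet count" is marked before treatment without a condition and during treatment with note 15, and is blank at follow-up. Note 1 sets the on-treatment frequency as "Weekly during radiotherapy". Note 15 reads "Only if concomitant chemotherapy is part of the treatment". Sections 6.1 to 6.4 let the last platinum dose fall up to a week after radiotherapy and require acceptable neutrophils and platelets before each dose, so such a dose brings one further count.

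**Toxicity list.** Section 5.12.1 grades acute and late effects by CTCAE 4.0 as set out in Appendix 1. That list includes anemia, white cell, neutrophil and platelet decreases, and febrile neutropenia. The platelet item is defined as "A finding based on laboratory test results that indicate a decrease in number of platelets in a blood specimen".

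**Analysis.** Objective 2.2 is "To determine the nature and prevalence of side effects at different time intervals" and to relate them to pretreatment function, dose and volume. Section 10.3.2 splits patients into grade 0-2 (or none) versus grade 3+ and tests this against a two-level dose measure. It adds: "Patients will also be grouped dichotomously by the number of side effects experienced". That count is compared with dose category and toxicity category by Chi-square or Fisher's exact test. The section gives no item list, time window, cut-point for the count or for dose, or separation by regimen.

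**The concern.** A side effect defined by a laboratory value is found when someone draws blood. On treatment, the plan schedules this weekly in one regimen and not at all in the other, then pools both in a comparison meant to describe how radiation dose relates to toxicity.

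The regimen is not assigned independently of dose. Section 6 gives chemotherapy for T3 disease, for more advanced nodal disease, or for extracapsular extension. Nodal extent also drives dose to the neck. Under 5.3.4, levels II and III on the side of a positive node go into CTV2, prescribed 63 Gy in Table 6. Table 6 gives the lowest dose level to contralateral levels III and IV, but treats each side as ipsilateral when both sides are involved. Patients in a higher dose category may therefore also be those on platinum and under weekly testing, and a difference produced by the drug or the testing could be reported as an effect of radiation dose.

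For prevalence over time, the blood-count items can fall after radiotherapy simply because scheduled testing has stopped.

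**Working it through.** The plan states no figure on this point, so there is none to reproduce. The check reads the schedule against the toxicity list, then sizes the effect under stated assumptions.

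**1. Share of the list.** Appendix 1 has 31 CTCAE rows, taking radiation recall and radiation dermatitis as the single row they share. Blood-count-dependent rows: febrile neutropenia, anemia, white cells, neutrophils, platelets. 5 / 31 = 16%. They overlap, since one low neutrophil count can contribute to three of them.

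**2. Scheduled counts after baseline.** Weekly over 7 weeks gives about 7 in a chemotherapy patient, plus one if a dose falls in the week after radiotherapy. An IMRT-alone patient has 0. In follow-up both have 0.

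**3. Recorded prevalence on treatment.** Assume a true prevalence t in all patients, a chemotherapy share c, and no unscheduled detection. Recorded prevalence over all patients = t × c.
- t = 20%: 0.20 × 0.30 = 6%; 0.20 × 0.50 = 10%; 0.20 × 0.70 = 14%.
- t = 40%: 12%, 20% and 28% for the same shares.
- With tested patients as denominator: t × c / c = t, whatever the share.

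**4. Dose comparison.** The documents give no haematologic rates, chemotherapy share or dose cut-point, so all of these are assumed. Setup: 30 patients in each dose group; four blood-count items, each with true probability q in every patient and seen only in chemotherapy patients; other side effects Poisson with mean m; count split at the pooled median; Fisher's exact test at 0.05; 2,000 simulations per row. There is no true dose effect and no drug effect, so any difference comes from testing alone.

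| Chemotherapy share, high v low dose | q | m | High-count proportion, high v low dose | False positives |
|---|---|---|---|---|
| 50% v 50% | 0.4 | 3 | 40.6% v 40.2% | 2.6% |
| 70% v 30% | 0.1 | 6 | 43.4% v 41.0% | 3.5% |
| 70% v 30% | 0.4 | 3 | 47.2% v 34.1% | 11.7% |
| 90% v 30% | 0.1 | 6 | 44.5% v 40.8% | 2.8% |
| 90% v 30% | 0.4 | 6 | 50.0% v 35.4% | 14.5% |
| 90% v 30% | 0.4 | 3 | 49.5% v 30.5% | 23.8% |
| 90% v 30%, all patients tested | 0.4 | 3 | 40.7% v 40.7% | 2.5% |

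The shift is nil when chemotherapy is balanced. In the unbalanced settings it runs from 43.4 − 41.0 = 2.4 points to 49.5 − 30.5 = 19.0 points. Because of its discreteness, Fisher's test here rejects only about 2-3% of the time when nothing is wrong.

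**5. Primary window.** Sections 10.1 and 10.3.1 score grade 3+ toxicity between six months and two years after treatment. The on-treatment counts, and any count in the week after radiotherapy, fall before that window, and neither regimen has a scheduled count within it.

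**The case against.** Scheduled testing is not the only way an event is recorded. Toxicity evaluation is scheduled for every patient during treatment and at follow-up, 5.12.1 has all events recorded, and nothing bars a count prompted by symptoms. A reader might infer that IMRT-alone patients cannot have a haematologic item recorded, or that prevalence must drop to zero when radiotherapy ends. The documents do not support either: every patient has a pretreatment count, unscheduled counts are possible, and some chemotherapy patients need a count after radiotherapy. What stands is that the chance of detection differs sharply by regimen and interval.

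The dose bias is conditional. Section 10.3.2 leaves the dose measure undefined, and it could be dose to a single organ. Both regimens use the same dose levels. The link through stage is also incomplete: N1 disease brings adjacent neck levels into CTV2 without bringing chemotherapy, and T3N0 disease does the reverse. A reader might infer that 10.3.2 is certain to give a spurious dose effect. The documents make an imbalance plausible but do not state one. Use of Appendix 1 for the count is likewise an inference from 5.12.1.

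Finally, platinum may itself lower blood counts and could affect non-laboratory items, so equal testing would not remove confounding by regimen. This is correct, and it makes stratification by regimen the main remedy and restriction of the item list the supplement.

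**Conclusion.** The point holds for the secondary analyses under objective 2.2 and section 10.3.2. As written, the dose comparisons mix any dose effect with the effect of chemotherapy and with unequal scheduled testing for 5 of 31 items.

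The size cannot be read from the documents. Under the assumptions above, the testing difference alone moves the high-count proportion by 0 points when chemotherapy is balanced across dose categories and by about 2 to 19 points in the unbalanced settings, with false positives from about 3% to 24%. The upper end needs a strong imbalance (90% v 30%) and frequent events (q = 0.4). A drug effect would be additional. The effect on recorded prevalence is more direct but confined to the blood-count items: a true 20% is recorded as 6% to 14% for chemotherapy shares of 30% to 70%, if unscheduled tests find nothing.

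A reader might extend this to the primary toxicity result. That does not follow, because the unequal testing is over before the six-month to two-year window opens. The change is worth making because it is cheap, not because the trial's main conclusion depends on it.

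**What to change.** Amend section 10.3.2 as follows.
- **Stratify by regimen.** Run the dose comparisons, both for the side-effect count and for grade 0-2 versus 3+, stratified by chemotherapy versus IMRT alone, for example with an exact stratified or Cochran-Mantel-Haenszel test.
- **Restrict the count.** Build the number of side effects from Appendix 1 items whose assessment is scheduled in all patients.
- **Report blood-count items separately.** Tabulate them by regimen and interval, with patients tested in that interval as the denominator, and list any events found by unscheduled tests so that none is lost.

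This needs analysis wording only: no new data, visits or tests. The cost is smaller strata and less power in a secondary, exploratory comparison. With 60 patients and an assumed chemotherapy share of 30% or 70%, the smaller stratum would have 60 × 0.30 = 18 patients before any split by dose.
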